## 5.2.2 Exclusion Criteria

A subject will not be eligible for study participation if he/she meets any of the following criteria:

1. Any prior systemic chemotherapy, small molecule inhibitors, immune checkpoint inhibitors, other monoclonal antibodies, antibody-drug conjugates, radioimmunoconjugates, T-cell or other cell-based or biologic therapies, or any other anti-cancer therapy than that described in Inclusion Criteria 3 – 5 for SCLC.

- 2. Any disease-directed radiotherapy (except PCI, palliative radiotherapy to a radiographically documented non-progressing lesion for symptom control, or preplanned radiotherapy for CNS metastases present prior to start of first-line therapy and non-progressing) after last dose of first-line chemotherapy.
- Any significant medical condition including any suggested by screening laboratory
  findings that in the opinion of the Investigator or Sponsor may place the subject at
  undue risk from the study.
- Documented history of a cerebral vascular event, unstable angina, myocardial infarction, or cardiac symptoms consistent with New York Heart Association (NYHA) Class III IV heart failure (refer to Appendix F) within 6 months prior to randomization.
- 5. Documented history of capillary leak syndrome.
- 6. Grade 2 or higher pleural or pericardial effusion within 4 weeks of randomization or earlier history of recurrent Grade 2 or higher effusions with ongoing requirement for pericardiocentesis or thoracentesis.
- 7. Serious infection within 2 weeks prior to randomization, including any Grade 3 or higher (per NCI CTCAE version 4.0) viral, bacterial, or fungal infection.
- 8. Female subject who is pregnant, breastfeeding or is considering becoming pregnant during the study or for approximately 6 months after the last dose of blinded investigational product.
- 9. Male subject who is considering fathering a child or donating sperm during the study or for approximately 6 months after the last dose of blinded investigational product.
- 10. Systemic therapy with corticosteroids at > 10 mg/day prednisone or equivalent within 1 week prior to randomization.
- 11. Subject has a history of active malignancies other than SCLC within the past 2 years prior to study entry, with the exception of in situ cancer which was curatively treated.

- 12. Any prior exposure to a pyrrolobenzodiazepine (PBD-based) or indolinobenzodiazepine-based drug, prior participation in a rovalpituzumab tesirine clinical trial, or known hypersensitivity or other contraindications to rovalpituzumab tesirine or excipient contained in the drug formulation.
- 13. Known hypersensitivity to biopharmaceuticals produced in Chinese hamster ovary cells.

### **Rationale for Exclusion Criteria**

- 1, 10-13 To select the appropriate subject population
- 2-7 For the safety of the subjects
- 8 9 The impact of rovalpituzumab tesirine on pregnancy in humans is unknown

### 5.2.3 Prior and Concomitant Therapy

[figure not shown]
Any concomitant medication or vaccine (including over-the-counter or prescription medicines, vitamins and/or herbal supplements) that the subject is receiving at the time of study drug administration or receives during the study through the safety reporting period (Section 6.1.5), must be recorded along with the reason for use, date(s) of administration including start and end dates, and dosage information including dose, route and frequency.

Any concomitant therapy given for a protocol-related AE should be recorded from the time of informed consent.

The AbbVie TA MD should be contacted if there are any questions regarding concomitant or prior therapies.

## 5.2.3.1 Prior Therapy

Subjects will have received first-line platinum-based chemotherapy consisting of 4 cycles of treatment with combination of either cisplatin or carboplatin with etoposide or

irinotecan; administration of Day 1 of the last cycle of first-line chemotherapy must be at least 3 weeks but no more than 9 weeks prior to randomization. Subjects previously treated for LD-SCLC are not eligible.

Subjects with central nervous system (CNS) metastases present prior to the initiation of first-line chemotherapy will have completed definitive local treatment (e.g., surgery or radiotherapy). Upon completion of first-line chemotherapy, subjects without a history of CNS metastases must have been offered prophylactic cranial irradiation (PCI), if offering this procedure is not contradictory to country or institutional guidelines. Subjects receiving PCI must complete it prior to randomization into the study. PCI regimen must be consistent with those endorsed by the National Comprehensive Cancer Network (NCCN) or European Society for Medical Oncology (ESMO).

[figure not shown]
## 5.2.3.2 Concomitant Therapy

All subjects enrolled will receive premedication consisting of dexamethasone/placebo. Refer to Section 5.5.1, Treatments Administered for details.

There are no other required concomitant therapies. However, due to the potential for rovalpituzumab tesirine-related skin photosensitivity, patients should be advised to avoid direct and indirect sun exposure as much as possible from Cycle 1 Day 1 until 30 days after the final dose. When sun exposure is unavoidable, patients should wear protective clothing and sunglasses, and use a broad-spectrum sunscreen and lip balm (SPF 30 or greater). Thirty-one to ninety days after last dose of Rova-T/placebo, the patient may resume outdoor activities with appropriate sun protection including broad brimmed hat, protective clothing and sunscreen SPF 30 or higher.

### 5.2.3.2.1 Allowed Concomitant Therapy

Standard supportive care for drug-related toxicity is permitted, including growth factors and blood product transfusions per local institutional standards. Other standard supportive care for symptom control or drug-related toxicity is allowed, such as analgesics, anti-emetics, electrolyte replacement, and hydration. Bone modifying agents

(e.g., bisphosphonates, denosumab) for bone metastases are also permitted per local institutional standards. Other prescribed medications for non-neoplastic conditions are allowed, as well as vitamins and nutritional supplements.

[figure not shown]
Concomitant prednisone (or equivalent) may be used at a dose of  $\leq 10$  mg/day. The use of intermittent high-dose corticosteroid treatment to prevent or manage infusion reactions, serosal effusions (see Section 6.1.8.1), or other non-cancer-related symptoms including premedication for known hypersensitivity reactions to contrast for scans is allowed.

Routine prophylaxis with vaccines is permitted; however, vaccines used should not contain live micro-organisms.

If the subject is taking chronic suppressive anti-infectives (antiviral, antifungal, or antibacterial), appropriate investigation must be completed prior to randomization, and documentation must exclude active infection. After exclusion of active infection, otherwise eligible subjects should complete or continue suppressive anti-infectives as prescribed.

If a subject requires palliative radiation during the study (e.g., symptomatic worsening of a bone lesion) diagnostic imaging has to be performed to assess for radiographic progression prior to radiation, and documentation of non-progressive status by radiography will be captured in the eCRF. Any cancer-directed therapy a subject receives due to disease improvement should be discussed with the TA MD in advance, if possible.

In the event of isolated CNS-only progression during study treatment, blinded investigational product may be withheld while local treatment is administered (e.g., radiotherapy) in accordance with institutional practice. Blinded investigational product may be restarted 1 week after the completion of local CNS disease-directed therapy.

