### Disease/Response Assessment (Radiographic Imaging)

Treatment response will be assessed by radiographic tumor evaluation per RECIST v1.1 at protocol-specified time points as outlined in the Appendix C, Study Activities. Diagnostic quality, spiral CT scan with contrast is recommended for all anatomic areas except brain (MRI is recommended for brain imaging); other CT methods or MRI for

respective anatomic areas may be used if performed consistently throughout the study for each individual subject and only under the circumstances described in Appendix G. Scans of the chest and abdomen must be obtained; scans of the neck and pelvis must also be obtained if there is documented or suspected involvement in these regions. Screening radiographic assessment must include brain MRI/CT. Diagnostic/baseline pre-first-line scans through screening scans will be reviewed by the investigator to determine disease response status per RECIST v1.1 for eligibility and stratification. On study disease response will be determined by the Investigator at each assessment according to RECIST v1.1 (Appendix G, Response Evaluation Criteria for Solid Tumors (RECIST) v 1.1)12 and independently reviewed by Central Radiographic Assessment Committee (described below). Disease/Response Assessment may be performed within 7 days prior to the Day 1 visit.

Effusion (pleural, pericardial, etc.) assessments will be performed by a radiologist at each on-study radiographic assessment and any new findings communicated to the Investigator prior to the next dose of blinded investigational product. Effusions should contribute to disease status assessment per RECIST v 1.1 only if confirmed malignant by cytology or otherwise clearly disease-related; if disease progression is suspected solely based on the appearance of new or increase of existing effusions, confirmation of malignant nature of such effusions is strongly recommended due to known adverse event profile of rovalpituzumab tesirine. If collected, effusion fluid must be tested for cytology if disease progression due to appearance/worsening of effusion is suspected.

Isolated CNS-only progression will not require removal of the subject from therapy. Refer to Section 5.2.3.2.1, Allowed Concomitant Therapy for details associated with CNS only progression.

The EOT assessment may be omitted if the previous assessment was performed within the preceding 6 weeks.

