Scheduled tumor assessments should not be affected by delays in therapy and/or drug holidays. Subjects will continue to be monitored by the same diagnostic method

throughout the study every 6 weeks after randomization, unless evidence of tumor progression warrants otherwise. In some cases, mandatory dose delays due to toxicity will lead to a gap between tumor assessment and dosing. In cases where this gap exceeds 1 week, the TAMD should be contacted for guidance.

Subjects who discontinue treatment for reasons other than radiographic disease progression will continue to be followed every 6 weeks from randomization to determine the extent of tumor burden, until disease progression occurs.

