### 5.4 Removal of Subjects from Therapy or Assessment

Each subject has the right to withdraw from study treatment at any time. In addition, the Investigator may discontinue a subject from the study treatment at any time for any reason if the Investigator considers it necessary. Each subject will be withdrawn from the study or study treatment (as applicable) per Section 5.4.1 if any of the following occur:

- The subject has radiographic progression according to RECIST v1.1 (with the exception of CNS-only progression).
- The subject requires cancer-directed radiotherapy or surgery related to clinical disease progression, or alternate anti-cancer agents during the study period. (Refer to Section 5.2.3.2.1, Allowed Concomitant Therapy for exceptions from this criterion).
- The subject experiences treatment toxicity which, in the Investigator's opinion, prohibits further therapy or the Investigator believes it is otherwise in the best interest of the subject.
- Subject is pregnant or begins breastfeeding during the treatment portion of the study.
- The subject decides to withdraw consent for any reason.
- Any other medical reason that AbbVie or the study Investigator deems appropriate.
- Significant non-compliance to the protocol.

Discontinued subjects will not be replaced.

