#### 5.5.4.2 Dose Modifications

### 5.5.4.2.1 Dose Treatment Delays due to Toxicity or Progression

Subjects who experience blinded investigational product-related toxicity during a cycle must have recovered as specified above before the next cycle may proceed. Any dose modifications except those indicated as mandatory below (including dose delay, reduction, resumption, and discontinuation) are to be performed at the discretion of the Investigator. Further guidelines suggesting dose modifications based on prior studies of rovalpituzumab tesirine are provided in Section 5.5.4.2.2, Dose Reduction Guidelines.

[figure not shown]
In cases of treatment delays of > 28 days, the TA MD should be contacted regarding the subject's continuation of treatment.

In the event of isolated CNS-only progression during study treatment, blinded investigational product will be withheld while local treatment is administered (e.g., radiotherapy) in accordance with institutional practice. Blinded investigational product may be restarted 1 week after the completion of local CNS disease-directed therapy. If more than 6 weeks have elapsed since the previous radiographic tumor assessment, the subject must undergo a radiographic tumor assessment to evaluate extracranial disease status prior to resuming blinded treatment. If additional sites of PD are present, the subject will be required to discontinue blinded investigational product.

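### For isolated CNS-only progression, Protocol 5.2.3.2.1 lets sites withhold study drug while 5.5.4.2.1 requires it and adds a restart scan, and the imaging section sends sites only to 5.2.3.2.1

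*Protocol*

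**What the plan says.** Two sections of the protocol tell sites what to do with blinded product when a subject progresses only in the CNS.

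- **5.2.3.2.1 (Allowed Concomitant Therapy):** "blinded investigational product may be withheld while local treatment is administered". On restart: "Blinded investigational product may be restarted 1 week after the completion of local CNS disease-directed therapy". It sets no imaging condition and does not cite 5.5.4.2.1.
- **5.5.4.2.1 (Dose Treatment Delays due to Toxicity or Progression):** "blinded investigational product will be withheld while local treatment is administered". The 1-week wait is the same. It adds that, if more than 6 weeks have passed since the previous tumor assessment, "the subject must undergo a radiographic tumor assessment to evaluate extracranial disease status prior to resuming blinded treatment". A subject with other sites of progression must stop.

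Three other places bear on which of these a site will read.

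- **5.3.1.1, Disease/Response Assessment:** CNS-only progression does not require removal from therapy, and "Refer to Section 5.2.3.2.1, Allowed Concomitant Therapy for details associated with CNS only progression". Section 5.5.4.2.1 is not named.
- **5.4 (Removal of Subjects):** CNS-only progression is exempt from the radiographic-progression criterion. For exceptions to the next criterion, on cancer-directed radiotherapy or surgery, it cites 5.2.3.2.1.
- **5.2.3.3 (Prohibited Therapy):** permitted radiotherapy is defined by reference to 5.2.3.2 and 5.2.3.2.1.

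**The concern.** One section permits what the other requires, for the same event and in nearly the same sentence. The cross-references lead to the permissive version. The product is a DNA cross-linking antibody-drug conjugate (3.3), and the question is whether to infuse it during or just after CNS radiotherapy. Sites could therefore treat the same event differently, and a site that relied on 5.2.3.2.1 could depart from 5.5.4.2.1 without knowing it.

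The shared 1-week wait does not close the gap. It applies to restarting, so a site that chose not to withhold has nothing to restart.

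**Working it through.** **Setting the texts side by side**

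| | 5.2.3.2.1 | 5.5.4.2.1 |
|---|---|---|
| Hold during local treatment | Permitted (*may*) | Required (*will*) |
| Restart 1 week after local therapy | Yes | Yes |
| Extracranial scan before restart | Not mentioned | Required (*must*) if more than 6 weeks since last assessment |
| Reference to the other section | None | None |

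**Is either text superseded?** No. The list of changes in Appendix K alters only the sentence on bone-modifying agents in 5.2.3.2.1 and touches neither CNS sentence. Both are current.

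**Does another rule settle it?** The dosing-day criteria in 5.5.4.1 cover neutrophils, platelets and resolution of product-related adverse events and laboratory abnormalities. None addresses ongoing CNS radiotherapy. No precedence rule places 5.5.4 above 5.2.3.2.1. Discontinuation for extracranial progression is already covered by 5.4, so that part is not in question.

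**When does the scan condition apply?** Imaging is every 6 weeks from randomization, and "Scheduled tumor assessments should not be affected by delays in therapy and/or drug holidays". On schedule, the 6-week limit is rarely passed, so the condition arises mainly when a scan is late. Because an assessment may be done up to 7 days before Day 1 (5.3.1.1), an early scan followed by an on-time one can also be 6 + 1 = 7 weeks apart.

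**Illustration of how often a dose would fall due**

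The documents give neither the number of CNS-only progressions nor the length of local treatment, so the number of affected subjects cannot be derived. The following assumes a treatment length D (weeks) and a start time uniform over the dosing pattern.

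- Cycles are 6 weeks and every third is omitted (5.1), so doses fall at weeks 0 and 6 of each 18-week pattern, 2 per 18 weeks.
- Under 5.5.4.2.1 no dose is given during local treatment or in the week after it, a window of D + 1 weeks.
- For D + 1 < 6 the window can contain at most one dose, so P(dose due in window) = 2(D + 1)/18 = (D + 1)/9.

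| D (assumed) | (D + 1)/9 |
|---|---|
| 1 day (1/7 week) | 1.143/9 = 0.127 |
| 1 week | 2/9 = 0.222 |
| 2 weeks | 3/9 = 0.333 |
| 3 weeks | 4/9 = 0.444 |

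The one-day case stands for a procedure such as surgery, which 5.2.3.1 names as a form of local treatment before entry. A simulation of 1,000,000 draws gave 0.127, 0.222, 0.333 and 0.445. The week after treatment contributes 1/9 = 0.111 in every row.

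**The case against.** The strongest reply is that the two sections can be obeyed together. A site that follows 5.5.4.2.1 also complies with 5.2.3.2.1, and dosing belongs to 5.5.4, not to the concomitant-therapy section. That is true, but nothing in the protocol says that 5.5.4 prevails, and the imaging section names 5.2.3.2.1 as the place for details of this event.

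A second reply is that 5.5.4.2.1 opens by leaving dose modifications to the investigator except where marked mandatory, that express mandatory labels attach to the toxicity reductions in 5.5.4.2.2, and that the hold is tied to institutional practice. This leaves some doubt about how binding *will* is. The reference to institutional practice appears in both CNS sentences, so it does not reconcile them. The scan instruction uses *must* and is binding on any reading.

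Two further points stand. With scans on time the scan requirement seldom applies, so it is the lesser part of this point. The percentages give the chance that a dose falls due, not that it is given. They do not include how often a site would choose not to withhold, and the final week matters only at a site that never withheld.

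**Conclusion.** The concern holds. The protocol is wrong as written: 5.2.3.2.1 and 5.5.4.2.1 give different instructions for isolated CNS-only progression, and the cross-reference in 5.3.1.1 leads to the less strict one. Severity is minor.

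This conclusion rests on the current wording alone. The 22% to 44% for 1 to 3 weeks of local treatment, and about 13% for a one-day procedure, are illustrations that depend on an assumed duration and a uniform start; the conclusion does not need them. The endpoint definitions and the sample size are unaffected.

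**What to change.** - In 5.2.3.2.1, change *may* to *will* for withholding during local treatment, and refer to 5.5.4.2.1 for the restart conditions.
- In 5.3.1.1, Disease/Response Assessment, add 5.5.4.2.1 to the cross-reference for CNS-only progression. Once 5.2.3.2.1 points there this second edit is less essential, but it takes the reader straight to the dosing rule.

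Sections 5.2.3.3, 5.4 and 5.5.4.2.1 need no change, since readers sent to 5.2.3.2.1 would then reach the restart rule through it.

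The cost is two wording changes. Section 9.1 requires IEC/IRB approval of any amendment, and nothing here needs an amendment of its own, so they can be carried in the next one made for other reasons.

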### 5.2.3.3 Prohibited Therapy

Subjects may not receive other investigational drugs, immunosuppressive medications, radiotherapy, or systemic anti-neoplastic therapy during the study, other than as allowed in Section 5.2.3.2 and Section 5.2.3.2.1. Additionally, strong inhibitors of cytochrome P450 3A4 (CYP3A4) should be avoided (refer to Table 1).

Table 1. Examples of Strong CYP3A4 Inhibitors

Enzyme/Transporter	Strong Inhibitor Examples 
CYP3A4	boceprevir, clarithromycin, cobicistat, conivaptan, danoprevir and ritonavir, diltiazem, elvitegravir and ritonavir, idelalisib, indinavir and ritonavir, itraconazole, ketoconazole, lopinavir and ritonavir, nefazodone, nelfinavir paritaprevir and ritonavir and (ombitasvir and/or dasabuvir), posaconazole, ritonavir, saquinavir and ritonavir, telaprevir, tipranavir and ritonavir, troleandomycin, voriconazole

[figure not shown]
(CYP) Cytochrome P450.

Note: This is not an exhaustive list; so if in question, please refer to the appropriate product label.

### 5.2.4 Contraception Recommendations

If female, subject must be either postmenopausal or permanently surgically sterile (refer to inclusion criteria for definitions of both) OR a Woman of Childbearing Potential (WOCBP), practicing at least one of the following methods of birth control, on randomization (or earlier) through at least 6 months after the last dose of blinded investigational product.

- Combined (estrogen and progestogen containing) hormonal contraception (oral, intravaginal, transdermal) associated with the inhibition of ovulation, initiated at least 1 month prior to randomization.
- Progestogen-only hormonal contraception (oral, injectable, implantable) associated with inhibition of ovulation, initiated at least 1 month prior to randomization

- Bilateral tubal occlusion/ligation.
- Bilateral tubal occlusion via hysteroscopy (i.e., Essure), provided a hysterosalpingogram confirms success of the procedure.
- Vasectomized partner(s), provided the vasectomized partner has received medical assessment of the surgical success and is the sole sexual partner of the WOCBP trial participant.
- Intrauterine device (IUD).
- Intrauterine hormone-releasing system (IUS).
- True abstinence: Refraining from heterosexual intercourse when this is in line with the preferred and usual lifestyle of the subject (periodic abstinence [e.g., calendar, ovulation, symptothermal, post-ovulation methods] and withdrawal are not acceptable).

If required per local practices, male or female condom with or without spermicide OR cap, diaphragm or sponge with spermicide should be used in addition to one of the birth control methods listed above (excluding true abstinence).

[figure not shown]
Male subjects who are sexually active with a WOCBP, even if the male subject has undergone successful vasectomy, must agree from randomization through at least 6 months after the last dose of blinded investigational product to use condoms and his female partner(s) must use at least one of the contraceptive measures (as defined in the protocol for female study subjects of childbearing potential).

Male subject agrees not to donate sperm from randomization through at least 6 months after the last dose of blinded investigational product.

